9.3 Secondary Endpoint(s)

The following key secondary endpoints will be analyzed for the ITT analysis set.

- The proportion of subjects in clinical remission at Months 2, 4, and 6, defined as a score of 0 for both rectal bleeding and stool frequency based on Clinical Response Score subset of the Clinical and Endoscopic Response Score
- Time to relapse, defined as number of days from randomization to the day of withdrawal due to escalation of therapy (i.e., surgical therapy, use of steroids, immunosuppressive or immunomodulating drugs, biologics, increase dose of 5 ASA in any form)

- The proportion of subjects with an increase from baseline in the Clinical and Endoscopic Response Score by 2 or more points in at least 1 component or by 1 or more points in at least 2 components at Month 6
- The change from baseline in serum CRP levels at Months 2, 4, and 6
- The change from baseline in fecal calprotectin levels at Months 2, 4, and 6

The proportion of subjects in clinical remission at Months 2, 4, and 6 will be analyzed by the generalized estimating equations (GEE) approach as longitudinal binary outcomes. The model will include the randomization strata, treatment, time, and treatment- by-time interaction. The clinical remission rates and odds ratio will be estimated for each time point. The overall treatment difference over 6 months will be estimated as the main effect for treatment in the model. The missing values will be imputed as non-remission, and an unstructured working correlation matrix will be used.

The time to relapse will be analyzed by the log-rank test stratified by the randomization strata. If a subject does not have the relapse by Day 168, the time to relapse will be censored at the earlier of the day that the last visit day or Day 168. The hazard ratio of relapse for mesalamine relative to placebo will be estimated (including the 95% CI) using the stratified Cox proportional hazards model with treatment group as a factor and the randomization strata as a stratification variable.

The proportion of subjects with an increase from baseline in the Clinical and Endoscopic Response Score by 2 or more points in at least 1 component or by 1 or more points in at least 2 components at Month 6 will be analyzed using the same statistical method used for the primary efficacy analysis.

The change from baseline in serum CRP levels and fecal calprotectin levels at Months 2, 4, and 6 will be analyzed by repeated-measures analysis of covariance (ANCOVA) models that include the randomization strata, treatment, time, and treatment-by-time interaction as fixed effects, and the corresponding baseline value as a covariate. The adjusted changes from baseline and their difference between treatment groups will be estimated for each time point. The overall treatment difference over 6 months will be estimated as the main effect for treatment in the model. The missing values will be left as missing, and an unstructured correlation matrix will be assumed.

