HRQoL	Health-related quality of life
IBDQ	Inflammatory Bowel Disease Questionnaire
ICH	International Conference on Harmonisation
ICMJE	International Committee of Medical Journal Editors
IEC	Independent Ethics Committee
IMP	Investigational medicinal product
IRB	Institutional Review Board

IRT	Interactive Response Technology
IVRS	Interactive Voice Response system
ITT	Intent-to-Treat
MedDRA	Medical Dictionary for Regulatory Activities
mITT	Modified Intent-to-Treat
Mo	Month
NIMP	Non-investigational medicinal product
NSAID	Nonsteroidal anti-inflammatory drug
PP	Per protocol
PT	Preferred term
QD	Once daily
SAE	Serious adverse event
SOC	System organ class
SUSAR	Suspected unexpected serious adverse reaction
TEAE	Treatment-emergent adverse event
UC	Ulcerative colitis
ULN	Upper limit of normal
US	United States
V	Visit
WHO-Drug	World Health Organization Drug Dictionary
Wk	Week

Definition of Terms

Remission	defined by the Clinical and Endoscopic Response Score as a score of 0 for rectal bleeding and 0 or 1 for stool frequency, with an endoscopic score of 0 or 1
Clinical remission	defined as a score of 0 for rectal bleeding and 0 or 1 for stool frequency based on clinical assessment subset of the Clinical and Endoscopic Response Score
Time to relapse	defined as number of days from randomization to the day of withdrawal due to escalation of therapy (i.e., surgical therapy, use of steroids, immunosuppressive or immunomodulating drugs, biologics, increase dose of 5-ASA in any form)

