4 SELECTION OF TRIAL POPULATION

4.1 Trial Population

4.1.1 Inclusion Criteria

1. Satisfied one of the following criteria for enrollment into the trial:
 - a. Met the remission criteria at Week 8 of Study 000174 (Pathway 1) *or*
 - b. Did not meet the remission criteria during Study 000174 and agreed to an additional 8 weeks of open-label treatment with mesalamine 4 g/day QD, after which met the remission criteria (Pathway 2) *or*
 - c. Subjects not currently enrolled in Study 000174 and currently treated with medications for UC and currently in remission <1 year based on clinical and endoscopic evaluation (rectal bleeding score of 0 and stool frequency scores of 0 or 1, with endoscopic score of 0 or 1 in Clinical and Endoscopic Response Score; i.e., clinical and endoscopic remission). The duration of prior remission must be less <1 year and include a history of flare (defined as escalation of medical therapy[ies]), and/or documented episode of recurrent rectal bleeding accompanied by abdominal pain and increased stool number that required medical intervention) (Pathway 3 – *de novo*)
2. Signed informed consent obtained before any trial-related procedures
3. Male or nonpregnant female subjects aged 18 to 75 years
4. Extent of colonic involvement historically confirmed (i.e., flexible sigmoidoscopy/colonoscopy report, colonoscopy report, biopsy reading) within past 12 months
5. Estimated creatinine clearance ≥ 60 mL/min
6. Females of childbearing potential must agree to use an adequate contraception during the course of the trial. Accepted forms of contraception are: i.e., implants, injectables, hormonal intrauterine device, combined hormonal contraceptives, sexual abstinence, and vasectomized sexual partner. Sterilized or postmenopausal women may also participate. Women must have a negative serum pregnancy test result at screening and negative urine pregnancy test result on baseline/randomization.

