2.2.2 Secondary endpoints

- The proportion of subjects in clinical remission at Months 2, 4, and 6, defined as a score of 0 for rectal bleeding and 0 or 1 for stool frequency based on Clinical Response Score subset of the Clinical and Endoscopic Response Score
- Time to relapse, defined as number of days from randomization to the day of withdrawal due to escalation of therapy (i.e., surgical therapy, use of steroids, immunosuppressive or immunomodulating drugs, biologics, increase dose of 5 aminosalicylic acid [5-ASA] in any form)
- The proportion of subjects with an increase from baseline in the Clinical and Endoscopic Response Score by 2 or more points in at least 1 component or by 1 or more points in at least 2 components at Month 6
- The change from baseline in serum CRP levels at Months 2, 4, and 6
- The change from baseline in fecal calprotectin levels at Months 2, 4, and 6
- The change from baseline to each scheduled assessment for published and validated domain scores of the IBDQ
- Safety assessed by incidence and severity of AEs and abnormal laboratory values

3 Trial design

This is a randomized, double-blind, placebo-controlled, parallel-group, multicenter, international, Phase 3 trial to investigate the safety and efficacy of mesalamine 2 g extended release granules (sachet) for maintenance of clinical and endoscopic remission in subjects with UC. Subjects who are in remission can be enrolled in the current trial via 1 of 3 pathways.

- Pathway 1: Subjects who are in remission following 8 weeks of double-blind treatment in Study 000174 can be randomized into Study 000175. The clinical and endoscopic remission criteria for Study 000174 include a Clinical and Endoscopic Response Score as a score of 0 for rectal bleeding and 0 or 1 with at least 1 point decrease from baseline for stool frequency, with an endoscopic score of 0 or 1.
- Pathway 2: Subjects in remission at the end of the 8-week open-label treatment period in Study 000174 will be allowed to be randomized into Study 000175.
- Pathway 3 – de novo: Subjects who did not participate in Study 000174 can also be enrolled; these subjects will have been treated with various medications for UC (excluding biologics and long-term [≥ 6 months] immunosuppressants) and will have been in remission for < 1 year. These de novo subjects will undergo a 72-hour mesalamine washout prior to entering the current trial and will have a Clinical and Endoscopic Response Score assessment to ensure eligibility.

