9.1 General Considerations

All statistical tests will be conducted at a two-sided 0.05 significance level.

All secondary endpoints will be tested without adjustment for multiplicity.

Randomization strata will be included in stratified analyses for efficacy endpoints. For the ITT, mITT, and PP analysis sets, randomization strata will be defined as follows:

- Stratum 1: Pathway 1 (mesalamine 4 g extended release granules arm in the 000174 trial)
- Stratum 2: Pathway 2
- Stratum 3: Pathway 3

Randomization strata for the all randomized analysis set will be defined as follows:

- Stratum 1: Pathway 1a (placebo arm in the 000174 trial)
- Stratum 2: Pathway 1b (mesalamine 4 g extended release granules arm in the 000174 trial)
- Stratum 3: Pathway 2
- Stratum 4: Pathway 3

Stool frequency and rectal bleeding scores at each visit will be calculated as an average of the daily scores collected within 5 days prior to the visit (excluding the visit day and the day before the visit day if the bowel preparation is needed on the day before the visit). If the daily scores in this period are available for fewer than 3 days, the average score will be considered missing. The average scores will be rounded to the nearest integer for the final score determination (e.g., 0.3 will be rounded to 0, and 0.5 will be rounded to 1). Handling of missing data in the statistical analyses will be described for each endpoint.

For the endoscopic assessment, the outcomes determined by the independent central reading procedure will be used for all analyses.

For visit-based data, the data collected on the day that is closest to the scheduled trial day within a window will be assigned to the corresponding analysis visit. [Table 2](#) shows the scheduled trial day and window for each analysis visit.

Table 2 Scheduled trial day and window for analysis visits

Analysis visit	Scheduled trial day	Window
Baseline	Day 1	prior to the first dose of IMP

Analysis visit	Scheduled trial day	Window
Week 2	Day 14	Day 1 to Day 35
Month 2	Day 56	Day 36 to Day 84
Month 4	Day 112	Day 85 to Day 140
Month 6	Day 168	Day 141 or after

If the closest day cannot be uniquely identified for an analysis visit, the data collected on an earlier trial day will be assigned to the analysis visit.

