9.2 Primary Endpoint(s)

9.2.1 Primary Variable(s) Analysis

The primary efficacy analysis will be based on the ITT analysis set. The proportion of subjects in remission, defined as rectal bleeding of 0 and stool frequency scores of 0 or 1 with an endoscopic score of 0 or 1 in the Clinical and Endoscopic Response Score at Month 6, will be assessed by the Mantel-Haenszel test stratified by the randomization strata at a two-sided 0.05 significance level. Subjects who discontinue the double-blind regimen before Month 6, as well as subjects with missing remission assessment at Month 6, will be considered not having met the remission criteria. The common odds ratio will be estimated using the Mantel-Haenszel adjusted odds ratio estimate, and its 95% confidence interval will be provided. The homogeneity of odds ratios across the randomization strata will be tested by the Breslow-Day test at a 0.05 significance level, and the odds ratio for each stratum will be presented in forest plots. The quantitative or qualitative nature of the possible treatment by stratum interaction will be assessed and discussed.

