9.2.2 Sensitivity Analyses

The following sensitivity analyses will be conducted to assess the robustness of the primary analysis:

- As-treated analysis based on actually received treatment
- Analysis on the all randomized analysis set
- Analysis on the mITT analysis set
- Analysis on the PP analysis set
- Analysis using the last observed Clinical and Endoscopic Response Score

The same analysis conducted for the primary analysis will be repeated for these sensitivity analyses.

Since the definition of remission was modified during the study, an analysis based on the original definition, i.e., rectal bleeding and stool frequency scores of 0 with an endoscopic score of 0 or 1 in the Clinical and Endoscopic Response Score, will also be conducted for reporting purpose.

In addition, sensitivity analyses using multiple imputation (MI) methods and pattern mixture models (PMMs) under missing at random (MAR) and missing not at random (MNAR) assumptions, respectively, will be conducted.

Under the MAR assumption, the missing stool frequency and rectal bleeding scores (Clinical Response scores) for Months 2, 4, and 6 will be imputed sequentially by regression-based imputation models using treatment group, baseline characteristics, and outcomes from preceding visits as the predictors. Once the missing Month 6 Clinical Response scores have been imputed, Month 6 Endoscopic Response score will be imputed by regression-based imputation models using treatment group, baseline characteristics, and Month 6 Clinical Response scores as the predictors. Based on the imputed Clinical and Endoscopic Response scores, the remission status at Month 6 will be determined. This imputation procedure will be repeated 100 times, and the primary analysis method will be applied to each of the imputed dataset. A combined estimate of the odds ratio for the treatment group compared to the control group and its 95% confidence interval will be obtained by the methods described in Rubin (1987)(6) .

Under the MNAR assumption, a similar MI method described above will be applied. However, in this analysis, only the data from the control group will be used for the regression-based imputation for Clinical Response scores at each visit and Endoscopic Response score at Month 6 by assuming that subjects from the treatment group will follow the same profile as the subjects on the control group after withdrawal from the study (Little & Yau, 1996(7); Ratitch & O’Kelly, 2011(8)).

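### SAP 9.3 analyses clinical remission with stool frequency 0 only, while SAP 2.2.2 and the protocol define the same endpoint with stool frequency 0 or 1

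*SAP*

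**What the plan says.** The SAP gives two definitions of the same secondary endpoint.

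- **SAP 9.3**, which sets out the GEE model, the imputation of missing values as non-remission and the estimates by visit, has clinical remission "defined as a score of 0 for both rectal bleeding and stool frequency". It is the first of the endpoints that this section calls key secondary.
- **SAP 2.2.2**, the endpoint list, has it "defined as a score of 0 for rectal bleeding and 0 or 1 for stool frequency based on Clinical Response Score subset".

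The protocol agrees with SAP 2.2.2 throughout. Its Definition of Terms has clinical remission "defined as a score of 0 for rectal bleeding and 0 or 1 for stool frequency based on clinical assessment subset", and the synopsis and sections 2.2 and 9.6.3 give the same rule.

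Three other places bear on the point. SAP 9.2.1 has the primary endpoint "defined as rectal bleeding of 0 and stool frequency scores of 0 or 1 with an endoscopic score of 0 or 1". SAP 9.2.2 adds an extra analysis of the primary endpoint: "Since the definition of remission was modified during the study, an analysis based on the original definition", where that definition required a stool frequency of 0. SAP section 12 says that the SAP does not depart from the analysis planned in the protocol.

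**The concern.** Section 9.3 is the section a programmer would code from. Taken literally, it produces remission rates and odds ratios at three visits for an endpoint that the protocol does not define.

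The result would also fit poorly with the rest of the trial. De novo subjects may enter with "rectal bleeding score of 0 and stool frequency scores of 0 or 1, with endoscopic score of 0 or 1", so someone can be randomized as being in remission and already lie outside the state that section 9.3 calls clinical remission. At Month 6, the secondary endpoint would be stricter on symptoms than the primary composite that contains the same two symptom scores.

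If section 9.3 stands, the statement in SAP section 12 is untrue. If section 12 stands, the wording of section 9.3 is wrong.

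**Working it through.** **1. The definitions side by side**

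| Place | Rectal bleeding | Stool frequency |
|---|---|---|
| Protocol synopsis, 2.2, 9.6.3, Definition of Terms | 0 | 0 or 1 |
| SAP 2.2.2 | 0 | 0 or 1 |
| SAP 9.3 | 0 | 0 |

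Five places agree and one differs. Section 9.3 is current text, not a change-log entry. The extra analysis in SAP 9.2.2 does not account for the difference: it includes an endoscopic score, so it concerns the primary composite and not clinical remission.

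**2. What this means for one subject**

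SAP 9.1 averages the daily scores over the 5 days before the visit, needs at least 3 days, and rounds: "0.3 will be rounded to 0, and 0.5 will be rounded to 1". With no bleeding, SAP 2.2.2 therefore requires a mean stool frequency below 1.5, and SAP 9.3 a mean below 0.5.

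| Diary (other days 0) | Mean | Rounded | SAP 2.2.2 | SAP 9.3 |
|---|---|---|---|---|
| Score 1 on 2 of 5 days | 0.4 | 0 | remission | remission |
| Score 1 on 2 of 4 days | 0.5 | 1 | remission | not in remission |
| Score 1 on 3 of 5 days | 0.6 | 1 | remission | not in remission |

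**3. Relation to the primary endpoint at Month 6**

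Under the protocol definition, anyone meeting the primary composite has bleeding 0 and stool frequency 0 or 1, and so is in clinical remission. The observed clinical remission proportion in the ITT set cannot then be below the primary proportion. Under section 9.3 it can be. This holds for observed proportions; GEE-adjusted rates need not obey it exactly.

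**4. Illustration of size**

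The documents give no expected clinical remission rate and no share of remitters with a stool frequency of 1. All inputs below are therefore assumptions: the primary planning rates of 68% and 49% (protocol 9.1, SAP 3.2) as a stand-in, 120 per arm, one visit, and an unstratified two-proportion test at two-sided 0.05 in place of the GEE.

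Power = Φ[(|p1 − p2| − 1.96·√(2·p̄(1 − p̄)/n)) / √(p1(1 − p1)/n + p2(1 − p2)/n)]

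Check against the plan: with p1 = 0.68, p2 = 0.49, p̄ = 0.585 and n = 120, this is Φ[(0.19 − 1.96 × 0.0636)/0.0624] = 0.852. That agrees with the stated power of at least 85% for the primary endpoint.

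Let s be the share of remitters with a stool frequency of 1. Each rate becomes p × (1 − s), and the number reclassified is 120 × (0.68·s_active + 0.49·s_placebo).

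| s active / placebo | Rates, % | Difference, points | Odds ratio | Power | Reclassified of 240 |
|---|---|---|---|---|---|
| 0 / 0 | 68.0 / 49.0 | 19.0 | 2.21 | 0.85 | 0 |
| 10% / 10% | 61.2 / 44.1 | 17.1 | 2.00 | 0.76 | 14 |
| 20% / 20% | 54.4 / 39.2 | 15.2 | 1.85 | 0.66 | 28 |
| 30% / 30% | 47.6 / 34.3 | 13.3 | 1.74 | 0.55 | 42 |
| 10% / 30% | 61.2 / 34.3 | 26.9 | 3.02 | 0.99 | 26 |
| 30% / 10% | 47.6 / 44.1 | 3.5 | 1.15 | 0.08 | 30 |

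Equal shares shrink the difference. Unequal shares can move it either way.

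**The case against.** The best reply is that the documents already show which definition governs. The protocol and SAP 2.2.2 agree, SAP section 12 declares no departure from the protocol, and SAP 9.2.2 identifies the rule requiring a stool frequency of 0 as the superseded definition of remission. On that reading, section 9.3 is a phrase missed when the definition changed, and a statistician reading the whole SAP would code 0 or 1. Harm arises only if someone coded from section 9.3 alone. The table shells are in a separate document (SAP section 14), so the programming is not known. Part of the SAP's front matter, next to its change log, was also not in the text available for this check and might state the intent.

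Much of this stands. Leftover wording is the likeliest explanation, though it is an inference. But a change-log note or an unseen shell would not alter the operative sentence in section 9.3, and the SAP should not leave its reader to choose between two definitions.

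The objection to the size figures is also fair. The rates are borrowed from a composite that includes endoscopy, so under the protocol definition true clinical remission rates should be at least as high. No power target was set for this endpoint, and the unequal shares have no basis in the documents. The table shows only that the direction is open. The entry criterion shows incoherence but does not itself enter any estimate, since the endpoint is assessed only at Months 2, 4 and 6.

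**Conclusion.** The concern holds: section 9.3 is wrong as written, because it contradicts both the SAP's own endpoint list and the protocol. This should be fixed. Confidence in the contradiction is high and rests on the text alone.

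The effect on the reported result is unknown in size and direction, and it arises only if section 9.3 was programmed literally. The scope is limited. The primary endpoint keeps stool frequency 0 or 1, and alpha and sample size do not depend on this text. SAP 9.1 also states that "All secondary endpoints will be tested without adjustment for multiplicity", so no later test hangs on this one.

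**What to change.** Before unblinding, replace the definition in SAP 9.3 with the one in SAP 2.2.2 (bleeding 0, stool frequency 0 or 1), and confirm that the table shells and the derivation of the variable use that rule.

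If the version requiring a stool frequency of 0 is also wanted, list it as a supplementary analysis under the original definition, as SAP 9.2.2 does for the primary endpoint, and record it in SAP section 12.

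The cost is one phrase in the SAP and a check of the shells. No new data are needed.

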9.4 Other Endpoint(s)

9.4.1 Health Related Quality of Life

The change from baseline in the IBDQ will be analyzed for the ITT analysis set.

The following domain scores for the IBDQ (Guyatt et al., 1989)(9) will be calculated by adding up scores from questions included in the domain for each subject at each time point:

- Bowel symptoms: Questions 1, 5, 9, 13, 17, 20, 22, 24, 26, 29
- Emotion function: Questions 3, 7, 11, 15, 19, 21, 23, 25, 27, 30, 31, 32

- Systemic symptoms: Questions 2, 6, 10, 14, 18
- Social function: Questions 4, 8, 12, 16, 28

The total score will be calculated by adding up all scores for each subject at each time point.

The handling of missing score in the calculation of the domain and total scores will be based on McMaster University (2010)(10). If there is only one missing response within a domain, the missing response will be imputed as an average of other responses within the domain. If there are two or more missing responses within a domain, the domain score will be considered missing.

If there are up to four missing responses, the missing responses will be imputed as an average of other responses. If there are more than four missing responses, the total score will be considered missing.

The change from baseline in the IBDQ domain and total scores at Months 2, 4, and 6 will be analyzed by repeated-measures ANCOVA models that include treatment, randomization strata, time, and treatment-by-time interaction as fixed effects, and the corresponding baseline value as a covariate. The adjusted changes from baseline and their difference between treatment groups will be estimated for each time point. The missing values will be left as missing, and an unstructured correlation matrix will be assumed.

10 Safety

